#### **9.1.2. Endpoints.**

##### **9.1.2.1. Primary endpoint.**

The primary endpoint is the per-lesion sensitivity and specificity for binary and dichotomized categorical features and the area under the ROC curve for ordinal and continuous features for the diagnosis of CRC metastases.

##### **9.1.2.2. Secondary endpoints.**

9.1.2.2.1. The areas under the ROC curves of multivariate models for diagnosis of CRC metastases.

9.1.2.2.2. Intraclass correlation coefficient between repeated quantitative measurements.

## **9.2 Specific Aims and Analysis Plans**

#### **9.1.3.1. Primary aim.**

9.1.3.1.1. Aim: For each MRI feature, estimate the per-lesion sensitivity and specificity (binary and dichotomized categorical features) or the area under the ROC curve (ordinal and continuous features) for the diagnosis of CRC metastases.

9.1.3.1.2. Analysis plan:

Frequency tables of the per-lesion MR features will be generated for non-continuous features. Descriptive statistics (e.g., mean, median, variance) will be used to summarize continuous features.

For each binary or dichotomized categorical feature, lesions will be classified as:

- True positive: lesion feature is positive and lesion histology is malignant
- False positive: lesion feature is positive and lesion histology is benign
- True negative: lesion feature is negative and lesion histology is benign
- False negative: lesion feature is negative and lesion histology is malignant

From this classification, the per-lesion sensitivity and specificity for the diagnosis of malignancy will be estimated. Corresponding 95% confidence intervals will be calculated using clustered data methods that can accommodate multiple lesions per patient and multiple observations per lesion.

For ordinal and continuous features, the ROC curve for the per-lesion diagnosis of malignancy will be generated and the area under the ROC curve calculated using empirical method. Corresponding 95% confidence intervals will be calculated using clustered data methods that can accommodate multiple lesions per patient and multiple observations per lesion. If the 95% confidence interval for the AUC contains the null hypothesis value of 0.5, then we will conclude that the corresponding feature does not have discriminatory ability.

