#### 6.11.3.2. Training.

The radiologist will be trained on a test set of 3T MR images obtained on non-study subjects. The test set will include examples of CRC metastases and benign lesions (hemangiomas, cysts, focal nodular hyperplasias, and transient hepatic intensity differences). During the training phase, the imaging criteria outlined below will be defined.

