#### 6.11.3.3. Interpretation.

The radiologist will review the nine image sets in a different random order in one reading session for each subject. (Reviewing each image set in a different session is not feasible). The random order of review will reduce bias in the performance of one image set relative to another. During the review of each image set, the radiologist will flag each detected nodule, number each new nodule consecutively, and characterize the corresponding nodule feature(s) as outlined in the Table below. If the radiologist identifies nodules on one image set that were missed on a prior image set, the radiologist will re-review the prior image set and retrospectively characterize the corresponding nodule features. The initial interpretations will be used for specific aim 1 and the final interpretations for specific aim 2. After the nine image sets are reviewed, the radiologist will review all the images in conjunction and score ten global lesion features. The radiologist also will score two per-patient features (anterioposterior skin-to-skin diameter of the abdomen [contiguous] and presence of ascites [four-point ordinal: none, mild, moderate, severe]), as these may conceivably affect image quality.

The research coordinator will enter the radiologist's per-lesion and per-patient interpretations into a data entry sheet. Representative screen capture images showing the

location and identifier of each lesion detected by the study radiologist will be exported in JPEG format. Under the radiologist's supervision, the research coordinator will place regions of interest on image sets 4-6 and record the T2\*, ADC, shear modulus values for each nodule and for each of the repeated acquisitions. Both repeated measurements will be used in the analysis of intraclass correlation coefficient. Only the first of the repeated measurements will be used in the sensitivity, specificity, and ROC analyses.

Image Set	Feature	Categories
1 T2w SSFSE	Signal intensity	Homogeneous 
 
• Markedly hypo-intense
 
• Hypo-intense
 
• Iso-intense
 
• Hyper-intense
 
• Markedly hyper-intense
 
 Heterogeneous
2 T2w FRFSE	Signal intensity	Homogeneous 
 
• Markedly hypo-intense
 
• Hypo-intense
 
• Iso-intense
 
• Hyper-intense
 
• Markedly hyper-intense
 
 Heterogeneous

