3 T1w SPGR	Signal intensity	Homogeneous 
 
• Markedly hypo-intense
 
• Hypo-intense
 
• Iso-intense
 
• Hyper-intense
 
• Markedly hyper-intense
 
 Heterogeneous
4 Six-echo SPGR	T2*	Continuous
5 DWI	ADC	Continuous
6 MRE	Shear modulus	Continuous
7 Dynamic 3D T1w	Kinetics	Homogeneous 
 
• With retention
 
• With fade
 
• With washout
 
 Ring 
 
• With retention
 
• With fade/washout
 
 Heterogeneous Puddles with retention
8 Late venous phase	Signal intensity	
 
• Hypo-intense
 
• Iso-intense
 
• Hyper-intense
 

9 Hepatocellular phase	Signal intensity	
 
• Hypo-intense
 
• Iso-intense
 
• Hyper-intense
 

Global	Long axis diameter	Continuous
	Short axis diameter	Continuous
	Shape	
 
• Round/oval
 
• Lobulated
 
• Irregular
 
• Geographic/polygonal
 
• Wedge
 
• Linear
 

	Margins	
 
• Sharp
 
• Mixed
 
• Indistinct
 

	Central heterogeneity	
 
• Yes, consistent with scar
 
• Yes, consistent with necrosis
 
• Yes, uncertain if necrosis or scar
 
• No
 

	Pseudo-capsule	
 
• Yes
 
• No
 

	Transient hepatic intensity difference	
 
• Yes – wedge shaped
 
• Yes – peri-lesional halo
 
• No
 

	Internal arteries	
 
• Yes
 
• No
 

	Draining veins	
 
• Yes
 
• No
 

	Edema around lesion	
 
• Yes
 
• No
 

	Distance from nearest surface	Continuous
	Overall confidence for cancer	
 
• 0 definitely not cancer
 
• 1 probably not cancer
 
• 2 possibly not cancer
 
• 3 indeterminate
 
• 4 possibly cancer
 
• 5 probably cancer
 
• 6 definitely cancer
 

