## **9.0 STATISTICAL CONSIDERATIONS**

### **9.1 Study Design and Endpoints**

#### **9.1.1. General study design.**

This is a prospective cohort pilot study assessing 3T MRI for diagnosis of CRC metastases to the liver in pre-hepatectomy patients. Consecutive eligible subjects with CRC metastases to the liver will undergo a research MRI of the liver within one week prior to curative hepatectomy done for clinical care. One radiologist will review the MR images and, for each focal lesion (benign or malignant) identified at imaging on each subject, assess 21 imaging features such as size, shape, margination, heterogeneity, kinetic enhancement pattern, and overall confidence for malignancy. Features will include binary, categorical, ordinal, and continuous variables. Sixteen features will be standard and five (T2\*, ADC, shear modulus, late venous phase signal intensity, and hepatocellular phase signal intensity) will be experimental. The MR sequences used to obtain the three quantitative experimental lesion features (T2\*, ADC, shear modulus) will be acquired twice for each subject. The radiologist also will assess two-per patient imaging features (abdominal AP diameter at the level of the portal vein bifurcation and the presence of ascites). Three demographic features (subject age, gender, ethnicity) will be available for the multivariate analyses; of the three, age will potentially be known to the radiologist as the scans will include the subject's date of birth.

For each subject, the lesions included in the analysis will be those identified at pre-hepatectomy imaging, *ex-vivo* imaging, pathology, or any combination of the three. The reference standard for each lesion will be the dichotomized histological diagnosis (malignancy versus other). Subjects are expected to have between one and ten CRC metastases in the hepatectomy specimen (average of three) and zero to five benign lesions (average of one). Subjects are not expected to have any malignancies other than CRC metastases.

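### A 95% CI for the AUC that contains 0.5 cannot show that an ordinal or continuous feature lacks discriminatory ability, because the AUC in scale order detects only monotone separation

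*Protocol*

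**What the plan says.** The analysis plan for the primary aim (Protocol Section 9.2, item 9.1.3.1.2) has two routes.

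- **Categorical route.** "For each binary or dichotomized categorical feature, lesions will be classified as" true or false positive or negative against histology, and sensitivity and specificity follow with clustered confidence intervals. No verdict rule is attached.
- **AUC route.** "For ordinal and continuous features, the ROC curve for the per-lesion diagnosis of malignancy will be generated and the area under the ROC curve" is obtained empirically, with a clustered 95% CI. A verdict rule is attached: if the interval "contains the null hypothesis value of 0.5, then we will conclude that the corresponding feature does not have discriminatory ability".

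Which features take which route is only partly fixed. Section 9.1.1 says "Features will include binary, categorical, ordinal, and continuous variables" without assigning individual features. The table in Section 6.11.3.3 marks six features as continuous: T2\*, ADC, shear modulus, the two diameters and the distance from the nearest surface. For "Late venous phase" (image set 8) and the hepatocellular phase (image set 9) it lists "Hypo-intense • Iso-intense • Hyper-intense". For image sets 1 to 3 it lists five intensity levels for homogeneous lesions plus one class outside that order: "Markedly hyper-intense Heterogeneous".

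Item 9.1.3.1.2 also plans frequency tables for non-continuous features and summary statistics for continuous ones. It does not say that these are split by histology.

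**The concern.** The empirical AUC is the probability that a random metastasis scores higher than a random benign lesion, with ties counted as one half. It departs from 0.5 only if one group tends to lie above the other. On a scale with a neutral value in the middle, one group can lie on both sides of the other. The two halves then cancel and the AUC sits near 0.5, although the individual levels carry diagnostic information.

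The benign class makes this conceivable. The reader's training set (Section 6.11.3.2) contains four quite different benign entities, and nothing in the protocol says they would all fall on one side of metastases.

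At stake is a primary-aim conclusion. The pilot is meant to inform a later trial (Sections 1.0 and 2.0), and a statement that an experimental feature does not discriminate would be a stronger finding than the analysis can give. Where the true scale-order AUC is 0.5, more lesions do not help: a 95% CI goes on containing 0.5 about 95% of the time.

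**Working it through.** **Inputs from the protocol.** Section 9.3 assumes 30 subjects, four lesions each on average, 75% malignant and within-subject correlation 0.5. That is 30 × 4 = 120 lesions, of which 90 are malignant and 30 benign. The protocol gives no distribution of any feature by histology, so the distributions below are assumptions.

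**The plan's own AUC figure.** Section 9.3 states 80% power to detect an AUC of 0.7. With design effect 1 + (4 − 1) × 0.5 = 2.5, the effective numbers are 90/2.5 = 36 and 30/2.5 = 12. The Hanley–McNeil variance at AUC 0.7 uses Q1 = 0.7/1.3 = 0.5385 and Q2 = 2 × 0.49/1.7 = 0.5765:

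(0.21 + 35 × 0.0485 + 11 × 0.0865)/(36 × 12) = 0.0066, so SE = 0.081.

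Then 0.2/0.081 ≈ 2.46. Power is 79% with one-sided alpha 0.05 (critical value 1.645) and 69% with two-sided alpha (1.96). Other variance formulas and other ways of handling clustering give other values. The figure concerns a true AUC of 0.7 and says nothing about a feature whose true AUC is near 0.5, so it does not bear on this point.

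**Formula.** With level probabilities p_M(i) for metastases and p_B(i) for benign lesions,

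AUC = Σ p_M(i) × [P_B(below i) + ½ p_B(i)].

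For one dichotomy, AUC = (sensitivity + specificity)/2.

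**Case 1: metastases 45/15/40%, benign 20/60/20% (hypo/iso/hyper).**
- Scale order: 0.45 × 0.10 + 0.15 × (0.20 + 0.30) + 0.40 × (0.80 + 0.10) = 0.045 + 0.075 + 0.360 = **0.480**.
- 'Not iso-intense': sensitivity 0.45 + 0.40 = **85%**, specificity **60%**, AUC (0.85 + 0.60)/2 = 0.725.
- Levels ordered by likelihood ratio (iso 0.25, hyper 2.00, hypo 2.25): 0.15 × 0.30 + 0.40 × 0.70 + 0.45 × 0.90 = **0.730**.

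**Case 2: metastases 10/80/10%, benign 45/10/45%.**
- Scale order: 0.10 × 0.225 + 0.80 × 0.50 + 0.10 × 0.775 = **0.500**.
- 'Iso-intense': sensitivity 80%, specificity 90%, AUC 0.85.
- Case 2 was simulated 2,000 times with 30 subjects, three malignant and one benign lesion each, latent within-subject correlation 0.5 and Obuchowski's clustered variance. The 95% CI of the scale-order AUC contained 0.5 in **93%** of trials. For the same feature dichotomized at the informative level, fixed in advance, it contained 0.5 in **0%**.

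**Counter-case, monotone: metastases 90/5/5%, benign 40/30/30%.**
- Scale order: 0.90 × 0.20 + 0.05 × 0.55 + 0.05 × 0.85 = **0.25**, or 0.75 with the scale reversed. This is far from 0.5, so a two-sided interval can exclude 0.5 from below. A relation that merely runs the other way is not missed.

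**The case against.** The case on the other side has four parts.

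1. **Reach.** A reader might infer that all five signal-intensity scales (image sets 1 to 3, 8 and 9) will be analysed by AUC. The protocol does not say so. It assigns none of them a type, and its feature table lists them under a column of categories. Sets 1 to 3 include heterogeneous lesions as a class outside the intensity order, so as listed they are not ordinal and fit the categorical route better. This stands. It leaves sets 8 and 9 as the natural candidates among the scales, and the continuous features as the certain ones.

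2. **Plausibility.** The distributions above were chosen to show the mechanism. The benign mix comes from a training set of non-study subjects, not from the study lesions. This also stands: the protocol neither predicts a non-monotone pattern nor rules one out.

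3. **Consequence.** A reader might infer that a useful feature would be dropped from the future trial, or that its direction of effect would be reported wrongly. Neither is supported. No section screens features on the univariate verdict, and the models of secondary aim 1 draw on all available features. An AUC near 0.5 asserts no direction, so the error would be a false null.

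4. **Placement.** Feature types and cut points are commonly left to a statistical analysis plan, and an empirical AUC for ordinal data is standard. Both are true. The verdict rule, however, is not an omission: it is written into the protocol and says more than the statistic can support. The planned frequency tables might reveal a non-monotone pattern, but the stated conclusion follows from the interval regardless.

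**Conclusion.** The point holds in a limited form. For any feature sent to the AUC route, an interval containing 0.5 shows at most that monotone discrimination was not demonstrated. It does not show absence of discriminatory ability.

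The rule applies for certain to the six features marked continuous, and most naturally also to the three-level scales of image sets 8 and 9. How large the error would be depends wholly on the true pattern. Under the assumed non-monotone patterns, a feature with sensitivity 80–85% and specificity 60–90% has a scale-order AUC of 0.48 to 0.50, and in the simulated case the rule calls it non-discriminating in 93% of trials of this size. Under a monotone pattern in either direction this particular error does not arise.

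The defect is in the wording of a primary-aim conclusion and is cheap to correct. It does not invalidate the AUC as a summary, and it does not show that any particular feature will be misjudged.

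**What to change.** In Section 9.2, item 9.1.3.1.2:

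- Replace the verdict for an interval containing 0.5 with a statement that monotone discrimination was not demonstrated. Apply this wording to every feature on the AUC route, so that no data-dependent exception is needed.
- State that the signal-intensity scales are handled by the existing categorical route: malignancy-pointing level or levels fixed before the study read, then clustered sensitivity and specificity. For image sets 8 and 9, report these beside any AUC that is kept.
- Show the distribution of each feature, continuous ones included, separately for malignant and benign lesions.

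The size and histological confirmation of the training set are not given, so the record should say on what basis each level was chosen.

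The cost is a few sentences and one advance decision per scale, with no new data or staff. The small downside is that a cut fixed in advance may not be the best one. If the relation proves monotone, little changes.

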The **primary aim** of this pilot study will be to estimate the per-lesion sensitivity and specificity for binary and dichotomized categorical MRI features and the area under the ROC curve for ordinal and continuous features MRI features for the diagnosis of CRC metastases, using the dichotomized histological diagnosis (CRC metastasis versus other) as the reference standard. Per-lesion co-localization of pre-operative imaging and pathology will be achieved by performing high-resolution *ex-vivo* MR imaging of the hepatectomy specimen prior to pathology sectioning

The **secondary aims** will be to:

- 1) estimate and compare the per-lesion area under the ROC curve of a multivariate model that uses experimental as well as standard MRI features versus that of a model that uses only standard MRI features for the diagnosis of CRC metastases.
- 2) estimate the intraclass correlation coefficient of repeated per-lesion quantitative measurements (T2\*, ADC, and shear modulus).

This pilot study will be used to plan a future clinical trial. The future trial will further assess the multivariate models and evaluate if 3T MRI is more sensitive and specific than 1.5T MRI and multidetector CT for diagnosing CRC metastases to the liver.

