#### **Primary aim:**

The primary aim is to estimate for each MRI feature the per-lesion sensitivity and specificity (binary and dichotomized categorical features) or the area under the ROC curve (ordinal and continuous features) for the diagnosis of CRC metastases, using the dichotomized histological diagnosis (CRC metastasis versus other) as the reference standard. Per-lesion co-localization of pre-operative imaging and pathology will be achieved by performing high-resolution *ex-vivo* MR imaging of the hepatectomy specimen prior to pathology sectioning

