### **9.3 Sample Considerations**

With an accrual of 30 subjects, this study will provide a worst-case precision (i.e., confidence interval half width) of  $\pm 18\%$  at a sensitivity of 50% and 5% significance level. The precision will improve the larger the observed sensitivity is from 50%. Furthermore, the observed precision will be better than 18% because some subjects will have multiple lesions.

Assuming 75% of lesions are malignant, an average of four lesions per subject, and a moderate correlation (0.5) between measurements within subjects, this study will have 80% power at a significance level of 0.05 to detect an AUC of 0.7 or higher.

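### The primary analysis attaches an AUC-versus-0.5 verdict to each of 7 to 13 features at an unadjusted 95% level, while the power statement covers a single AUC

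*Protocol*

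**What the plan says.** The aim is worded as estimation, feature by feature: "The primary aim is to estimate for each MRI feature the per-lesion sensitivity and specificity", or the AUC where the feature is ordinal or continuous (Section 3.0). Section 9.1.2.1 makes all of these the primary endpoint, including "the area under the ROC curve for ordinal and continuous features for the diagnosis of CRC metastases", and singles out no feature. Section 9.1.1 has the radiologist "assess 21 imaging features such as size, shape, margination, heterogeneity, kinetic enhancement pattern, and overall confidence for malignancy".

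The analysis plan for the primary aim (item 9.1.3.1.2) then specifies the intervals: "Corresponding 95% confidence intervals will be calculated using clustered data methods that can accommodate multiple lesions per patient". For AUC features it goes further and names a null value and a conclusion: "If the 95% confidence interval for the AUC contains the null hypothesis value of 0.5, then we will conclude that the corresponding feature" has no ability to discriminate. It says nothing about an interval that excludes 0.5.

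Section 9.3 states that "this study will have 80% power at a significance level of 0.05 to detect an AUC of 0.7 or higher". It does not say which feature this refers to, or that several will be examined.

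**The concern.** A study that only estimates would report AUCs with intervals and stop. This plan gives each feature a null hypothesis, a criterion and a verdict, and powers the study to detect a departure from the null. Applied to many features with no adjustment, such a rule carries a joint error rate well above the one significance level in the document. A reader who sees 0.05 in Section 9.3 could take it to describe the primary aim as a whole, which it does not.

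What is at stake is how the feature-level results are read. An interval that misses 0.5 by chance would probably be taken as evidence that the feature discriminates. The written half of the rule has its own cost: on the plan's own 80% power, a feature with a true AUC of 0.7 would be declared non-discriminating in 100% − 80% = 20% of studies.

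**Working it through.** **1. The plan's own figures.** Both figures in Section 9.3 describe one quantity at a time.
- Half width for one sensitivity of 50% with 30 subjects: 1.96 × √(0.25/30) = 0.179. The stated ±18% reproduces.
- Power for one AUC of 0.7 against 0.5: 30 × 4 = 120 lesions, 75% malignant, so 90 malignant and 30 benign. The answer depends on how clustering is handled. With the Hanley-McNeil variance and a Wald test, power is 79.2% (one-sided, design effect 1 + 3 × 0.5 = 2.5) or 78.7% (two-sided, design effect 1 + 2 × 0.5 = 2). Across the variance formulas tried, two-sided power is 55% to 69% at design effect 2.5 and 94% to 98% with clustering ignored. A simulation with a shared subject effect and a clustered AUC variance gave 99.7%. The 80% is reachable on some readings and is not disputed here; every version of it concerns one AUC.

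**2. How many features fall under the rule.** The table in Section 6.11.3.3 has 9 image-set rows and 12 global rows, 21 in all. The protocol does not list which are ordinal.
- Strict count, 7: T2\*, ADC, shear modulus, the two diameters, distance from the surface, and the seven-level confidence score.
- Broad count, 7 + 6 = 13: adding late venous signal, hepatocellular signal, margins, and the signal-intensity scales of image sets 1 to 3. Those three scales also contain a heterogeneous level that has no place in the ordering, so 13 is the generous end.

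**3. Chance that at least one interval excludes 0.5 when all k features are uninformative.** Each 95% interval acts as a two-sided test at 0.05.
- Independent features: 1 − 0.95^k. For k = 7, 1 − 0.698 = 30.2%. For k = 13, 1 − 0.513 = 48.7%.
- Equal correlation ρ between the features' test statistics: 1 − ∫ φ(t) [Φ((1.96 − √ρ·t)/√(1−ρ)) − Φ((−1.96 − √ρ·t)/√(1−ρ))]^k dt.

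| ρ | k = 7 | k = 13 |
|---|---|---|
| 0 | 30.2% | 48.7% |
| 0.3 | 27.1% | 41.8% |
| 0.5 | 23.0% | 33.4% |
| 0.7 | 17.8% | 24.1% |
| 0.9 | 11.4% | 13.8% |

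The values of ρ are assumptions. The 0.5 in Section 9.3 is a correlation between measurements within a subject, not between features, and cannot be used here.

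**4. Sensitivity.**
- With only six features uninformative, the chance is 26.5% at ρ = 0, 20.7% at 0.5 and 10.8% at 0.9.
- If directions were fixed in advance and only intervals wholly above 0.5 counted, independence would give 1 − 0.975^7 = 16.2% and 1 − 0.975^13 = 28.0%. The written rule is two-sided.
- Expected number of chance exclusions, whatever the correlation: 7 × 0.05 = 0.35, or 13 × 0.05 = 0.65.

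**The case against.** The strongest reply is that this is a single-arm pilot whose aim is to estimate, feature by feature. Each feature answers its own question, no overall 5% error rate is promised, and unadjusted intervals are normal in such work. Choice of adjustment and exploratory labelling can also be left to a statistical analysis plan. Most of this stands. The lack of a lead feature or an adjustment would be no fault in a plan that only estimated. What remains is that the protocol itself states a null value, a verdict and a power, and so steps outside estimation.

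Three stronger readings are tempting, and the documents do not support them.
- A reader might infer a flat false-positive rate of 23% to 33% in place of a promised 5%. Those figures need an assumed between-feature correlation of 0.5 and every feature uninformative, including a trained liver radiologist's overall confidence score. The protocol never claims 5% across features.
- A reader might infer that falsely flagged features are what passes to the next trial. Section 1.0 says only "This pilot study will be used to plan a future clinical trial" and that the multivariate models will be assessed further there. The plan for secondary aim 1 builds its full models from all available features, so the AUC rule is not a gate.
- A reader might infer that features could give opposite answers about 3T MRI. Comparison with 1.5T MRI and CT is deferred to the future trial, so there is no overall verdict here to contradict.

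**Conclusion.** The point holds in a limited form. Item 9.1.3.1.2 attaches a formal verdict to each of 7 to 13 features at an unadjusted 95% level, and Section 9.3 gives power at 0.05 for one AUC, so 0.05 is a per-feature level. With all tested features uninformative, the chance of at least one interval excluding 0.5 is about 11% to 49%. This rests on equally correlated, approximately normal test statistics with correlation 0 to 0.9, and on the two feature counts. It falls as more features truly discriminate. Reading such an interval as proof of discrimination is implied by calling 0.5 a null value and by powering to detect 0.7, but it is not written. The weight is modest for a pilot. The change is still worth making, because it alters what the trial may conclude and costs almost nothing.

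**What to change.** In item 9.1.3.1.2, delete the per-feature conclusion. State that all per-feature AUCs, sensitivities and specificities are exploratory estimates with 95% confidence intervals not adjusted for multiplicity. In Section 9.3, say that the 80% power at 0.05 is for a single feature before any adjustment.

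This takes a few sentences and no new data, readers or subjects, and every estimate is still reported. The downside is that the pilot can then claim neither discrimination nor its absence for any feature.

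Only if the sponsor wants to keep a discrimination claim is more needed: either one lead AUC named in advance with the power statement tied to it, or Holm-adjusted p-values across the AUC features. Holm costs power. Its first step uses 0.05/7 = 0.0071 or 0.05/13 = 0.0038. With the Hanley-McNeil variance (null variance for the threshold), two-sided power for an AUC of 0.7 at that step falls from 94.2% to 75.7% or 67.6% with clustering ignored, and from 54.6% to 22.5% or 16.0% at design effect 2.5. A stricter threshold would also leave more features non-significant, so the negative conclusion should be deleted in either case.
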